Appendix E Schedule1: Laboratory procedures for HIV-uninfected participants

				Visit	1	2	3	4 ¹	5 ¹	6 ¹	7	8 ¹	9 ¹	10	11	12	13	14	15	16 17	_
				Day		D0	D84	D168	D169	D182-196	D273	D364	D378-394	D455	D546	D637	D728	D819	D910 D	001 D109	2
				Week	Screening visit ³	W0	W12	W24	·	W26-28	W39	W52	W54-56	W65	W78	W91	W104	W117	W130 V	143 W15	 غ
				Month	want	MO	M3	M6		M6.5-7	M9	M12	M12.5-13	M15	M18	M21	M24	M27	M30 I	133 M36	
						Ad26.Mos4.HIV or Placebo	Ad26.Mos4.HIV or Placebo	Ad26.Mos4.HIV + gp140/Alum or Placebo				Ad26.Mos4.HIV + gp140/Alum or Placebo									
_	12	Assay	Tube	Tube size																	Total
Procedure BLOOD COLLECTION	Ship to 1,2	location ²	Type	(vol. capacity)			l						1		1						
Screening/Diagnostic																					
Screening HIV test	Local lab	Local lab	SST	5mL	5				T	T	Г — Т		T _	Τ	T	Υ	Τ				5
	HSML-NICD /	HSML-NICD /			 		ļ	ļ	 				·	 	ļ						
HIV diagnostics ⁸	UW-VSL	UW-VSL	EDTA	10mL	-	10	10	10	-	10	10	10	-	10	10	10	10	10	10	10 20 ⁸	150
Safety labs																					
Hemoglobin	Local lab	Local lab	EDTA	5mL	5	_	_	5	_	_	I - I	5	_	I –	_	-	T -	_	-	_ _	15
STI Serology								***************************************													***************************************
Syphilis 15	Local lab	Local lab	SST	5mL	 	5 ¹⁵	_	5 ¹⁵		T -	T - T	5 ¹⁵	T -	Ι –	5 ¹⁵		5 ¹⁵	_	5 ¹⁵	- 5 ¹⁵	35
ARV detection by serum or plasma ^{9, 10}	BARC	TBD	SST	8.5mL	l –	у	_	у	i –		1	у	 	T	у	i –	у	_	у	— у	0
ARV detection by dried blood spots 11	BARC	HVTN Labs	EDTA	2mL	İ						See foots	note 11		i	å		A	i			0
Immunogenicity & virologic assays ⁵		L			A	ś															
Host genetics ⁶	BARC	HVTN Labs	Na Hep	10mL	I –	20	_	_	T -	T -	T = T		T -	Ι _	T -	Ī —	Ι _	_	- 1	_ _	20
Cellular assays		L			L	i		i		d				i	i		L	l			
ICS	BARC	HVTN Labs	Na Hep	10mL	I –	50	T _		T –	50	Ι _ Ι	50	50	Τ_	50	T -	50		50	_ 50	400
IFN-g ELISpot	BARC	HVTN Labs	Na Hep	10mL	l	30		_	_	30	1	30	30	 	30	 	30	_		_ 30	
Humoral assays	27110	L			i		L	i	i	1	J			1	1	i	1	i			
Binding Ab	BARC	HVTN Labs	SST	8.5mL	T	8.5	T			8.5	Т _ Т	8.5	8.5	Т	8.5	T	8.5		8.5	- 8.5	68
Neutralizing Ab	BARC	HVTN Labs	SST	8.5mL	 	8.5		_	-	8.5		8.5	8.5	 _	8.5		8.5			_ 8.5	
Env-specific ELISA	BARC		SST		ļ	8.5		_	- -	8.5		8.5	8.5		8.5	į	8.5	ļ			
		Janssen		8.5mL			ļ		ļ		-	8.5	··	ļ	ģ						0
Ad26 neutralizing Ab	BARC	Janssen	SST	8.5mL	ļ	у	ļ		ļ		-			ļ —	 	ļ	ļ  				
Antibody-dependent cellular phagocytos	BARC	HVTN Labs	SST	8.5mL		у		L		у	1 – 1	y	у	L	у	 	у		у	_ у	0
Innate Immunity						·	·	·	·	Ţ	,			·	y		Ţ	·			
RNA gene expression	BARC	HVTN Labs	Tempus	3mL	ļ -	3		3	3	ļ -	-			ļ —	 	ļ	ļ				
Serum cytokines	BARC	HVTN Labs	SST	8.5mL		8.5	_	8.5	8.5		-			ļ	 	 	ļ —	_			26
Transcriptional profiling	BARC	HVTN Labs	Na Hep	10mL		40	_	40	40		-	_		ļ —		ļ —				_ _	120
Viral isolation/sequencing ⁹	BARC	TBD	EDTA	10mL		10	10	10		10	10	10	20 ¹³	10	10	10	10	10	10	10 10	160
STORAGE						,		ç	·y	·	ş			·	ç	.,	· · · · · · · · · · · · · · · · · · ·	y			,
PBMC	BARC		Na Hep	10mL		100				100		50	100		50		50	-	50	_ 50	550
Serum	BARC		SST	8.5mL		42.5		_		42.5	-	17	42.5		17	_	17	_	17	17	213
Visit total					10	347	22	84	54	270	22	205	270	22	200	22	200	22	200	22 210	2178
56 Day total ¹²					10	357	22	84	137	407	22	205	475	22	200	22	200	22	200	22 210	
URINE COLLECTION																					
Pregnancy test ⁷	Local lab	Local lab			х	x	x	x	_	_	-	x	_	l –	-	-	_	-	-	× –	
EITHER URINE OR CERVICAL/VAGINAL SWAB CO	OLLECTION																				***************************************
Urine - Chlamydia/Gonorrhea ¹⁶	Local lab	Local lab			Ī –	X ¹⁷	_	X ¹⁷	T -	T -	I – I	X ¹⁷		T -	X ¹⁷	-	X ¹⁷	-	X ¹⁷	— X ¹⁷	
Cervical/vaginal swab -	Local lab	Local lab				X ¹⁷	_	X ¹⁷	· — —		1 – I	X ¹⁷		T	X ¹⁷	 	X ¹⁷	_	X ¹⁷	— X ¹⁷	
Chlamydia/Gonorrhea ¹⁶					 				 						1		T	 		^	
CERVICAL/VAGINAL SWAB COLLECTION									~	T	,	40					T				
Trichomonas vaginalis 18	Local lab	Local lab				X ¹⁸		X ¹⁸				X ¹⁸		 	X ¹⁸		X ¹⁸		X ¹⁸	— X ¹⁸	
MUCOSAL COLLECTIONS		·			·	·	·	 		·	·			·	·	-9	·	y			
Vaginal swab	BARC	TBD				X	_	X				X			х		х	_			
Cervical secretions	BARC	HVTN Labs			_	X	_	X	_	_	_	X	_	l —	X	l –	X	- 1	_ 1	_ ! _	

¹BARC = Bio Analytical Research Corporation South Africa (Pty) Ltd (Johannesburg, South Africa); HSML-NICD = HIV Sero-Molecular Laboratory-National Institute for Communicable Diseases (Johannesburg, South Africa); UW-VSL = University of Washington Virology Specialty Laboratory (Seattle, Washington, USA)

²HVTN Laboratories include: Cape Town HVTN Immunology Laboratory (CHIL, Cape Town, South Africa); South Africa); South Africa Immunology, Laboratory—National Institute for Communicable Diseases (SAIL-NICD, Johannesburg, South Africa); Fred Hutchinson Cancer Research Center (FHCRC, Seattle, Washington, USA); Duke University Medical Center (Duke, Durham, North Carolina, USA); University of Cape Town, South Africa), University of Colorado Denver (Aurora, Colorado, USA) Non-HVTN laboratory: Janssen = Janssen Prevention and Vaccines (Leiden, The Netherlands) TBD = Laboratories to be determined by the HVTN laboratory Program

³Screening may occur over the course of several contacts/visits up to and including day 0 prior to vaccination

⁴Local labs may assign appropriate alternative tube types for locally performed tests

Immunogenicity assays will be performed at M0 (for binding antibody assay), M7 and M13 Based on the number of responders observed at these timepoints, lab assays may be performed on participants for humoral and cellular responses at other timepoints Genotyping may be performed on enrolled participants using cryopreserved PBMC collected at baseline, initially in participants who demonstrate vaccine-induced T-cell responses at postvaccination timepoints

Pregnancy test must be performed on the day of vaccination with negative results received prior to vaccination Persons who have undergone total hysterectomy or bilateral oophorectomy (verified by medical records) are not required to undergo pregnancy testing

HVTN 705/VAC89220HPX2008, Version 4.0 / FINAL

- 8At an early termination visit for a withdrawn or terminated participant (see Section 911), blood should be drawn for HIV diagnostic testing, as shown for visit 17 above
- ⁹EDTA blood collected for plasma may also be used for ARV detection, if necessary
- ¹⁰Testing plan for ARV detection to be determined
- 11EDTA blood for dried blood spots will be collected on regularly scheduled calendar days throughout the study Refer to the Specimen Collection SSP for more information
- 12 The total 56-day blood collection includes 2mL EDTA blood collection for dried blood spots. It is highly improbably that the 2mL EDTA blood collection will occur at every possible timepoint, but it is reflected in the blood draw totals for every visit to account for this extreme possibility
- ¹³EDTA blood collected for viral isolation/sequencing may also be used for HIV diagnostics, if necessary
- ¹⁴Based on hemoglobin levels at visits 4 and 8, blood draws at visits 5, 6 and 9 may be reduced Refer to the Specimen Collection SSP for more information
- 15Syphilis testing will be done by serology and will be performed at visits 2, 4, 8, 11, 13, 15 and 17; in addition, testing may occur at any other visit if clinically indicated
- 16 Chlamydia/gonorrhea testing will be done with either urine or cervical/vaginal swabs Either urine or swab is acceptable, and clinics will determine which specimen will be collected and tested
- ¹⁷Chlamydia/gonorrhea testing will be performed at visits 2, 4, 8, 11, 13, 15 and 17; in addition, testing may occur at any other visit if clinically indicated
- 18 Cervical/vaginal swab will be collected for Trichomonas testing at visits 2, 4, 8, 11, 13, 15 and 17; in addition, testing may occur at any other visit if clinically indicated
- y = SST blood collected for humoral assays and serum storage will also cover specimen needs for ARV detection, Ad26 neutralizing antibody, and antibody-dependent cellular phagocytosis; no separate blood draw is needed

Appendix E (continued) Schedule1: Laboratory procedures for HIV-uninfected participants, extension phase

				Visit	18	19	20	21	22	23	24	
				Month	M39	M42	M45	M48	M51	M54	M57	
		Assay	Tube	Tube size								Total
Procedure	Ship to 1,2	location ²	Type ³	(vol. capacity) ³			-					Total
BLOOD COLLECTION				***************************************								
Diagnostic						3						
HIV diagnostics ⁸	HSML-NICD / UW-VSL	HSML-NICD / UW-VSL	EDTA	10mL	10	10	10	10	10	10	10	90
Safety labs						···········			***************************************			
Hemoglobin	Local lab	Local lab	EDTA	5mL	_	-	_	_	-	_	_	0
STI Serology												
Syphilis ⁸	Local lab	Local lab	SST	5mL	_	5	-	5	-	5	_	35
ARV detection by serum or plasma	BARC	TBD	SST	8.5mL		у		у	_	у	_	0
ARV detection by dried blood spots 5	BARC	HVTN Labs	EDTA	2mL				See footnote 5				0
Immunogenicity & virologic assays												
Cellular assays												
ICS	BARC	HVTN Labs	Na Hep	10mL	_	50	_	50	-	50	_	150
IFN-g ELISpot	BARC	HVTN Labs	Na Hep	10mL	_	30	_	30	-	30	_	90
Humoral assays												
Binding Ab	BARC	HVTN Labs	SST	8.5mL	_	8.5	_	8.5	_	8.5	_	26
Neutralizing Ab	BARC	HVTN Labs	SST	8.5mL	_	8.5	_	8.5	-	8.5	_	26
Env-specific ELISA	BARC	Janssen	SST	8.5mL	_	8.5	_	8.5	_	8.5	_	26
Antibody-dependent cellular phagocytos	BARC	HVTN Labs	SST	8.5mL	_	у	_	у	-	у	_	0
Viral isolation/sequencing ⁷	BARC	TBD	EDTA	10mL	10	10	10	10	10	10	10	90
STORAGE								·	······································	***************************************	·	
PBMC	BARC		Na Hep	10mL	_	50	_	50	_	50	_	150
Serum	BARC		SST	8.5mL	_	17	_	17	-	17	 	51
Visit total	,				22	200	22	200	22	200	22	687
56-Day total ⁶					22	200	22	200	22	200	22	
EITHER URINE OR CERVICAL/VAGINAL SWAB CO	OLLECTION											
Urine - Chlamydia/Gonorrhea ⁹	Local lab	Local lab			_	x		x	_	×	_	
Cervical/vaginal swab - Chlamydia/Gonorrhea ⁹	Local lab	Local lab			_	х	_	×	_	×	_	
CERVICAL/VAGINAL SWAB COLLECTION							 		A			
Trichomonas vaginalis 10	Local lab	Local lab				X		×	T	×		

1BARC = Bio Analytical Research Corporation South Africa (Pty) Ltd (Johannesburg, South Africa); HSML-NICD = HIV Sero-Molecular Laboratory-National Institute for Communicable Diseases (Johannesburg, South Africa); UW-VSL = University of Washington Virology Specialty Laboratory (Seattle, Washington, USA)

- 3 Local labs may assign appropriate alternative tube types for locally performed tests
- 4 EDTA blood collected for plasma may also be used for ARV detection, if necessary
- 5EDTA blood for dried blood spots will be collected on regularly scheduled calendar days throughout the study Refer to the Specimen Collection SSP for more information
- 6The total 56-day blood collection includes 2mL EDTA blood collection for dried blood spots. It is highly improbable that the 2mL EDTA blood collection will occur at every possible timepoint, but it is reflected in the blood draw totals for every visit to account for this extreme possibility
- 7EDTA blood collected for viral isolation/sequencing may also be used for HIV diagnostics, if necessary
- 8Syphilis testing will be done by serology at visits 19, 21, and 23; in addition, testing may occur at any visit if clinically indicated
- 9Chlamydia/gonorrhea testing will be performed at visits 19, 21 and 23; in addition, testing may occur at any visit if clinically indicated Chlamydia/gonorrhea testing will be done with either urine or cervical/vaginal swab. Either urine or swab is acceptable, and clinics will determine which specimen will be collected and tested
- 10Cervical/vaginal swab will be collected for Trichomonas testing at visits 19, 21, and 23; in addition, testing may occur at any visit if clinically indicated
- y = SST blood collected for humoral assays and serum storage will also cover specimen needs for ARV detection, and antibody-dependent cellular phagocytosis assays; no separate blood draw is needed

² HVTN Laboratories include: Cape Town HVTN Immunology Laboratory (CHIL, Cape Town, South Africa); South African Immunology Laboratory–National Institute for Communicable Diseases (SAIL-NICD, Johannesburg, South Africa); Fred Hutchinson Cancer Research Center (Seattle, Washington, USA); Duke University Medical Center (Durham, North Carolina, USA); University of Cape Town (Cape Town, South Africa); University of Colorado Denver (Aurora, Colorado, USA) Non-HVTN laboratory: Janssen = Janssen Prevention and Vaccines (Leiden, The Netherlands) TBD = Laboratories to be determined by HVTN Laboratory Program

Appendix F Schedule 2: Laboratory procedures for HIV-infected participants

				Visit:	#.X ^{4, 5}	Visit:	31	32	
						Weeks after diagnosis ⁸ :	W12	W24	
						Month:	M3	M6	
Procedure	Ship to ¹²	Assay location ²	Tube Type ³	Tube size (vol. capacity) ³					Total
BLOOD COLLECTION	,		71	(
Screening/Diagnostic							~~~~~		***************************************
HIV diagnostics	HSML-NICD / UW-VSL	HSML-NICD / UW-VSL	EDTA	10mL	20 ⁶		_	-	20
HIV PCR viral load	HSML-NICD / UW-VSL	HSML-NICD / UW-VSL	EDTA	10mL	_		10	10	20
CD4+T cell count	Local lab	Local lab	EDTA	5mL	5		5	5	15
Immunogenicity & virologic assays									
Cellular assays									
ICS	BARC	HVTN Labs	Na Hep	10mL	50		50	50	150
IFN-g ELISpot	BARC	HVTN Labs	Na Hep	10mL	20		20	20	60
Humoral assays									
Binding Ab	BARC	HVTN Labs	SST	8 5mL	8 5		8 5	8 5	25.5
Neutralizing Ab	BARC	HVTN Labs	SST	8 5mL	8 5		8 5	8 5	25.5
Env-specific ELISA	BARC	Janssen	SST	8 5mL	у		у	у	0
Antibody-dependent cellular phagocytosis	BARC	HVTN Labs	SST	8 5mL	у		у	у	0
Viral isolation/sequencing	BARC	TBD	EDTA	10mL	10		10	10	30
STORAGE									
PBMC	BARC		Na Hep	10mL	50		50	50	150
Plasma	BARC		EDTA	10mL	10		10	10	30
Serum	BARC		SST	8 5mL	17		17	17	51
Visit total					199		189	189	577
56-Day total					199		189	189	
URINE COLLECTION									
Pregnancy Test ⁹	Local lab	Local lab			_		Х	х	
MUCOSAL COLLECTION									
Vaginal swab	BARC	TBD			X ⁷		_	_	

¹BARC = Bio Analytical Research Corporation, South Africa (Pth) Ltd (Johannesburg, South Africa); HSML-NICD = HIV Sero-Molecular Laboratory-National Institute for Communicable Diseases (Johannesburg, South Africa); UW-VSL = University of Washington Virology Specialty Laboratory (Seattle, Washington, USA)

²HVTN Laboratories include: Cape Town HVTN Immunology Laboratory (CHIL, Cape Town, South Africa); Fred Hutchinson Cancer Research Center (FHCRC, Seattle, Washington, USA); Duke University Medical Center (Duke, Durham, North Carolina, USA) Non-HVTN laboratory: Janssen = Janssen Prevention and Vaccines (Leiden, The Netherlands) TBD = Laboratories to be determined by the HVTN laboratory Program

³Local labs may assign appropriate alternative tube types for locally performed tests

⁴Visit # X indicates a Redraw visit where # is a Schedule 1 visit number Confirmatory draw for HIV diagnostics will be collected at the Redraw visit should occur as soon as possible after the clinic receives a Redraw Request from the HIV diagnostics laboratory Multiple subsequent Redraw visits may be necessary; only the EDTA blood specimen for HIV diagnostics, viral isolation/sequencing, and plasma storage will be collected at the subsequent Redraw visits

⁵If the first Redraw visit is preceded by visit 2, 6, 8, or 9, in Schedule 1, the clinic should contact HVTN Lab Ops immediately prior to scheduling the participant for the Redraw visit HVTN Lab Ops will provide guidance on what blood specimens to collect in order to not exceed the 56-day blood volume limit

⁶One tube will remain as a whole blood specimen and be shipped ambient to the HIV diagnostics laboratory; it should not be processed for plasma by the site-associated laboratory. The other tube will be processed for plasma as usual

⁷Vaginal swab will only be collected at the first Redraw visit

⁸Date of diagnosis = date of initial specimen draw that led to first Redraw Request

⁹Persons who have undergone total hysterectomy or bilateral oophorectomy (verified by medical records), are not required to undergo pregnancy testing

y = SST blood collected for humoral assays and serum storage will also cover specimen needs for Env-specific binding Ab and antibody-dependent cellular phagocytosis; no separate blood draw is needed

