10.3 HIV-1 testing postvaccination

Surveillance for HIV-1 takes place at vaccination visits and follow-up visits specified in Appendix E and Appendix G.

In-study HIV testing will be performed according to the HVTN HIV diagnostic testing algorithms. Routinely, specimens are initially assayed with an HVTN Lab Program—approved HIV 1/2 enzyme immunoassay (EIA) or chemiluminescent microparticle immunoassay (CMIA). If the EIA/CMIA is reactive, nucleic acid polymerase chain reaction (PCR) test to detect HIV-1 RNA will be performed as indicated in the algorithm. The algorithm is repeated on a second specimen to confirm a diagnosis of HIV-1 infection. The second specimen for confirmatory testing may be collected at an interim visit (designated as visit #.X, where # is the visit at which the first reactive test was obtained and X designates the interim visit; specified in Appendix F and Appendix H). Samples to be stored for future immunogenicity or virology studies will also be collected at this time (Appendix F).

A 'case' will be defined as a participant with confirmed detectable HIV-1 nucleic acid PCR on 2 different specimen collection dates. The nucleic acid test will most commonly be the HIV-1 RNA PCR viral load test. Confirmation of HIV-1 infection will be determined as dictated by the HVTN HIV testing algorithm (available on the HVTN 705 protocol-specific website). Before issuing an HIV-1 infection report for a participant diagnosed with HIV-1 infection prior to study unblinding, all testing results will be reviewed by a blinded, independent Endpoint Adjudicator(s) and/or designee(s) (Section 10.4).

If a participant is confirmed to have become HIV-1 infected prior to study unblinding, plasma HIV-1 viral RNA will be measured on archived samples collected according to Appendix E. In addition to plasma HIV-1 viral RNA testing, participants may also have measurements of immunogenicity assessments and a clinical assessment performed at all postinfection visits (see Appendix F).

The HVTN Laboratory Program is responsible for all in-study diagnostic HIV testing.

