10.4 Endpoint adjudication

The diagnostic criteria for HIV-1 infection outside the setting of a vaccine trial are well accepted. However, definitive diagnosis of HIV-1 infection in the context of having received an HIV vaccine that is even partially effective may be more difficult. Specifically, if the immune responses elicited by vaccination are capable of completely suppressing viral replication, or if vaccination alters the normal serological response upon exposure to HIV-1, standard diagnostic tests may be more difficult to assess. Therefore, the HVTN will have an endpoint adjudication process to assess all serological and virological testing, in a blinded manner, on each participant in the trial who, prior to study unblinding, tests positive per the HVTN 705 HIV-1 diagnostic testing algorithm. The assessment of the Endpoint Adjudicator(s) or designee(s) will be reported to the SDMC and to the HIV diagnostics laboratory.

The Endpoint Adjudicator(s) and/or designee(s) must notify the SDMC within 1 working day of any confirmed HIV-1 infection. The HIV diagnostics lab will inform the clinic of the outcome of the HIV testing algorithm (ie, HIV infected, HIV uninfected, or redraw required).

The Endpoint Adjudicator(s) and/or designee(s) will be an expert in the fields of infectious diseases or laboratory medicine independent of the clinical investigators participating in this trial.

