11.2 Total blood volume

Required blood volumes per visit are shown in Appendix E and Appendix F. Not shown is any additional blood volume needed if additional testing were required, or if a serum pregnancy test needs to be performed. The additional blood volume would likely be minimal. The total blood volume drawn for each participant will not exceed 500 mL in any 56-day (8-week) period.

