- Item 7 Updated in Appendix A, Sample informed consent form and Appendix C, Sample consent form for use of samples and information in other studies: SAHPRA contact information
- Item 8 Updated with changes described in Letter of Amendment 1 dated May 6, 2019
- Item 9 Updated with changes described in Clarification memo 1 dated March 08, 2019
- Item 10 Version history updated in Section 14

Date: May 06, 2019

Protocol version: Version 3.0

Protocol modification: Letter of Amendment 1

Item 1 Revised in Section 7.3.1, *Delaying vaccinations for a participant*, Section 7.3.2, Participant departure from vaccination schedule, and Section 7.3.3, Discontinuing vaccination for a participant: guidance regarding vaccination out of window

Date: March 08, 2019

Protocol version: Version 3.0

Protocol modification: Clarification memo 1

Item1 Revised in Section 9.10, *Visit windows and missed visits*: Missed Visit form completion

Date: July 26, 2018

Protocol version: Version 3.0

Protocol modification: Full Protocol Amendment 2

- Item 1 Added in Section 4.3, *Clade C gp140*: Clade C gp140 (L-Histidine buffer) study product to be mixed with aluminum phosphate adjuvant by the pharmacist
- Item 2 Corrected in Section 9.4, Follow-up visits, Section 9.8, Pregnancy prevention assessment, and Appendix G, Schedule 1:Procedures at HVTN CRS for HIV-uninfected participants: pregnancy prevention assessment timepoints
- Item 3 Added in Appendix G, Schedule 1:Procedures at HVTN CRS for HIV-uninfected participants: behavioral risk assessment timepoints at month 7 and month 36
- Item 4 Corrected in Appendix F, *Laboratory procedures for HIV-infected participants*, footnote 5: visits in Schedule 1 that may affect redraw guidance.
- Item 5 Corrected in Appendix E, Schedule 1:Laboratory procedures for HIV-uninfected participants, footnote 14 and Appendix G, Procedures at HVTN CRS for HIV-uninfected participants, footnote 8: hemoglobin assessment and potential blood draw adjustment visits
- Item 6 Added in Section 3, *Overview*, and Appendices E and F, *Laboratory Procedures*: UW-VSL as a backup laboratory for HIV diagnostics
- Item 7 Updated in Section 11.1, *HVTN CRS laboratory procedures*: source for guidelines concerning the clinical and processing laboratories

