² Specimens collected at the enrollment visit may be obtained within the 14 days prior to vaccination, except for a pregnancy test which must be performed on the day of vaccination with negative results received prior to vaccination

³ For specimen collection requirements, see Appendix E

⁴ Pregnancy prevention assessment is required only for participants who are capable of becoming pregnant

⁵ Includes pre-test counseling A subsequent follow-up contact is conducted to provide post-test counseling and to report results to participant

Schedule 1: Procedures at HVTN CRS for HIV-uninfected participants during extension phase

Extension phase visit:	18	19	20	21	22	23	24	Post
Month:	M39	M42	M45	M48	M51	M54	M57	
Study procedures ¹								
Abbreviated physical exam	X	X	X	X	X	X	X	
Risk reduction counseling	X	X	X	X	X	X	X	
Behavioral risk assessment questionnaire	_	_	_	X	_	_	_	_
Social impact assessment	X	X	X	X	X	X	X	
Concomitant medications	X	X	X	X	X	X	X	
Intercurrent illness/adverse experience	X	X	X	X	X	X	X	_
HIV infection assessment ²	X	X	X	X	X	X	X	
Confirm HIV test results provided to participant	X	X	X	X	X	X	X	X
Local lab assessment								
GC/CT		X	_	X	_	X		
Syphilis	_	X	_	X	_	X	_	_
Trichomonas vaginalis	_	X	_	X	_	X	_	
Poststudy								
Unblind participant	_	_	_	_	_	_	_	X

¹ For specimen collection requirements, see Appendix E, Table for Extension phase.

⁶ Pregnancy test must be performed on the day of vaccination with negative results received prior to vaccination Pregnancy test to determine initial eligibility may be performed at screening, but must also be done on day 0 prior to first vaccination Persons who have undergone total hysterectomy or bilateral oophorectomy (verified by medical records), are not required to undergo pregnancy testing

⁷ Must be performed prior to vaccination

⁸ Based on hemoglobin levels at visits 4 and 8, blood draws at visits 5, 6, and 9 may be reduced, respectively Refer to the Specimen Collection SSP for more information

⁹ Specimen collection required at vaccination visits must be performed prior to vaccination; however, it is not necessary to have results prior to vaccination, except for results of a pregnancy test, if indicated

¹⁰ Reactogenicity assessments are performed as described in Section 9 9

¹¹May be performed offsite

² Includes pre-test counseling. A subsequent follow-up contact is conducted to provide post-test counseling and to report results to participant.

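### Appendix F footnote 5 omits visits 4 and 5, although a redraw between visits 5 and 6 followed by a full visit 6 draw totals 606 mL against the 500 mL limit

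*Protocol*

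**What the plan says.** Section 11.2 of the protocol states that the volume drawn from each participant "will not exceed 500 mL in any 56-day (8-week) period". Appendix E prints a running 56-day total for each scheduled visit, and Appendix F gives the volume of the redraw visit used to confirm an HIV diagnosis.

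Footnote 5 of Appendix F links the two schedules. If "the first Redraw visit is preceded by visit 2, 6, 8, or 9, in Schedule 1", the clinic must contact Lab Ops before scheduling the redraw and is told which specimens to take so that the 56-day limit is kept. Footnote 4 says the redraw "should occur as soon as possible after the clinic receives a Redraw Request from the HIV diagnostics laboratory".

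Section 10.3 numbers a redraw by the visit of origin, "where # is the visit at which the first reactive test was obtained". Section 10.4 lists the possible results of the testing algorithm as "HIV infected, HIV uninfected, or redraw required", so a redraw does not always end Schedule 1.

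The Appendix E and G footnotes offer one route to smaller draws: "Based on hemoglobin levels at visits 4 and 8, blood draws at visits 5, 6, and 9 may be reduced". That route depends on hemoglobin, not on whether a redraw was taken.

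**The concern.** Visit 4 carries a 10 mL HIV diagnostic sample, so a redraw arising from it is foreseeable. It is followed by visit 5 one day later and by visit 6, one of the largest draws in the schedule, 14 to 28 days after visit 4. A redraw taken promptly can therefore fall between visits 5 and 6.

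The word preceded in footnote 5 can mean the visit with the reactive sample (visit 4) or the visit immediately before the redraw (visit 5). Neither is listed, so neither reading prompts the call to Lab Ops. At stake is a participant safeguard: a woman who is cleared, or whose status is still open, could give a full redraw and a full visit 6 draw without anyone having been told to plan the two together. No efficacy endpoint or analysis is affected.

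**Working it through.** **Inputs.** Tube volumes come from Appendix E (Schedule 1) and Appendix F (redraw). As the protocol does in its own totals, 2 mL for dried blood spots is added at each Schedule 1 visit. Appendix E footnote 12 says of this allowance: "It is highly improbably that the 2mL EDTA blood collection will occur at every possible timepoint".

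**Volumes per visit (mL).**
- Visit 4, Day 168: 10 + 5 + 5 + 3 + 8.5 + 40 + 10 + 2 = 83.5
- Visit 5, Day 169: 3 + 8.5 + 40 + 2 = 53.5
- Visit 6, Day 182-196: 10 + 50 + 30 + 25.5 + 10 + 100 + 42.5 + 2 = 270
- First redraw: 20 + 5 + 50 + 20 + 8.5 + 8.5 + 10 + 50 + 10 + 17 = 199

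**Reproducing the plan's figures.** Visits 4 + 5 + 6 = 83.5 + 53.5 + 270 = 407, the 56-day total printed at visit 6. The redraw sum of 199 matches Appendix F.

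**Adding the redraw between visits 5 and 6.**
- Up to and including the redraw: 83.5 + 53.5 + 199 = 336, leaving 500 − 336 = 164 for visit 6.
- After a full visit 6: 336 + 270 = 606, which is 106 over (106/500 = 21%).
- Without the three dried-blood-spot allowances: 606 − 6 = 600, which is 100 over (20%).
- If visit 5 was missed: 83.5 + 199 + 270 = 552.5, still over.

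The span from Day 168 to Day 196 is 28 days, so all four draws share one 56-day window whichever day the redraw is done.

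**Comparison with the listed visits.** The table takes a redraw before the next scheduled visit.

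| Visit before redraw | Total at the redraw | Total after the next large draw | Listed? |
|---|---|---|---|
| 2 (with screening) | 356.5 + 199 = 555.5 | not needed | yes |
| 5 (reactive sample at 4) | 336 | 606 (with visit 6) | no |
| 6 | 407 + 199 = 606 | not needed | yes |
| 8 | 204.5 + 199 = 403.5 | 403.5 + 270 = 673.5 (with visit 9) | yes |
| 9 | 474.5 + 199 = 673.5 | not needed | yes |

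Visit 8 is the informative row. At the redraw the total is within the limit and it is exceeded only when visit 9 follows. The redraw between visits 5 and 6 has the same shape.

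For a redraw 7 to 21 days after the visit (an assumed range, since turnaround is not given), the other visits stay under 500: 221 after visits 3, 7, 10, 12, 14 and 16; 398.5 after visits 11, 13 and 15; 408.5 after visit 17. Visits 3 and 7 would become a problem only with redraw delays of at least 43 and 50 days, which the instruction to redraw promptly makes unlikely.

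**The case against.** The strongest reply is that footnote 5 concerns the redraw, and the redraw here reaches only 336 mL. The excess arises at visit 6, which Appendix E governs, and the footnote does not say that it plans later scheduled draws. That purpose is inferred from the listing of visit 8. There is another possible reason for that listing: visit 9 has no scheduled HIV diagnostic draw, so a redraw taken after visit 9 on a reactive visit 8 sample is still numbered from visit 8 and itself reaches 673.5 mL. This alternative does not rescue the list. Under the same numbering, a redraw from visit 4 taken after visit 6 itself reaches 606 mL, and visit 4 is still not listed.

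Four other points stand and limit the finding:
- Section 11.2 has no exception, so a site that follows it must cut visit 6.
- The Study Specific Procedures and Site Lab Instructions named in Section 11.1 are not among the documents and may already handle this.
- The chain of events is narrow. Women confirmed infected before visit 6 move to Schedule 2, and the documents give no basis for estimating how often the rest occurs.
- Visits 4 and 5 describe one scenario, not two. Visit 5 has no HIV diagnostic draw and matters only as the visit nearest the redraw.

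**Conclusion.** The concern holds as a minor omission. The protocol's printed totals are correct; the visit list in footnote 5 is incomplete. A first redraw between visits 5 and 6, followed by a full visit 6 draw, gives 606 mL against 500 mL (600 mL without dried blood spots). This rests on three conditions: the redraw falls in that interval, the woman is cleared or unresolved at visit 6, and visit 6 is drawn in full. It is a missing prompt, not permission to exceed the limit. The arithmetic is certain; the look-ahead purpose is an inference, though no reading of the footnote explains listing visit 8 while leaving out both 4 and 5. The version history in Section 14 (Full Protocol Amendment 2, Item 4) records an earlier correction to "footnote 5: visits in Schedule 1 that may affect redraw guidance", so the sponsor has already treated this list as worth getting right.

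**What to change.** Extend the list in footnote 5 to visits 2, 4, 5, 6, 8 and 9. Add one clause stating that for visits 4, 5 and 8 the Lab Ops guidance covers the redraw together with the next scheduled large draw (visit 6 or visit 9).

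The choice of tubes can stay with Lab Ops. For the redraw before visit 6, storage tubes alone can absorb the 106 mL: visit 6 stores 100 + 42.5 = 142.5 mL, and the redraw stores 50 + 10 + 17 = 77 mL. No tube assigned to a listed assay need be cut.

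The cost is two visit numbers, one clause and a memo to sites. No procedure is added. The only loss is an occasional smaller storage sample.
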